9.1.3 Part B

Participation in Part B is optional. After the last Part A Visit, subjects will be followed off-treatment at a visit scheduled every 4 weeks (\pm 2 weeks) to assess the change in proteinuria after stopping administration of VX-147 (Table 3-3). Part B visits will continue until the UPCR level reaches \geq 90% of baseline levels or 3 months after the last dose of study drug, whichever occurs first. If a subject has not achieved \geq 90% of baseline UPCR by the Part B Week 12 Visit, the Part B Week 12 Visit will be the last study visit.

Subjects will not be allowed to participate in Part B if (1) their UPCR level during Part A remained \geq 90% of baseline or (2) their UPCR level reached \geq 90% of baseline before the Part A Week 13 Visit and remained at that level through the Week 13 Visit.

The SFUV and Part B Week 4 Off-treatment Follow-up Visit may occur on the same day, provided the visit windows for both visits are met.

9.2 Method of Assigning Subjects to Treatment Groups

This is an open-label study. All subjects will receive VX-147.

9.2.1 Replacement Subjects

Subjects may be replaced at the discretion of Vertex.

9.3 Rationale for Study Elements

9.3.1 Study Design

The study will be single-arm and open-label. All subjects will receive VX-147 for a total of 13 weeks. A placebo arm was not included because FSGS is a rare, severe disease with a very low likelihood of spontaneous remission. ¹⁵⁻¹⁷ This is the first study targeting the APOL1 pathway

in patients with FSGS, so the duration required for proteinuria levels to reach nadir is unknown. Clinical practice guidelines 18 for other therapies indicate that ≥ 4 months of therapy may be required for patients with nephrotic-range proteinuria to achieve complete remission (defined as UPCR <0.3 g/g). The duration of 13 weeks for this study was selected to allow the maximum treatment time supported by nonclinical data.

This is the first study in patients with FSGS, therefore subjects will receive 2 dose levels of VX-147 to characterize PK of VX-147 at 2 dose levels in this population. As shown in Figure 9-1, the 15 mg qd dose will be administered for 2 weeks and the 45 mg qd dose will be administered for 11 weeks. The 2-week duration for the 15 mg qd dose was selected based on an exposure-response model suggesting that a measurable decrease in proteinuria may be observed after 2 weeks of dosing. The 11-week additional duration for the 45 mg qd dose, provides a total of 13 weeks continuous dosing, which is the longest observation period supported by available nonclinical data.

9.3.2 Study Population

The study will enroll male and female subjects, aged 18 to 65 years old, with biopsy proven FSGS, 2 *APOL1*-risk alleles, and nephrotic-range proteinuria. These patients have need for new treatments, because patients with FSGS and nephrotic-range proteinuria have rapid progression to kidney failure, with mean renal survival less than 10 years. The presence of FSGS on biopsy will be confirmed by an independent, external expert (Section 9.3.6) to determine eligibility.

9.3.3 Study Drug Dose

The administration of once daily doses of 15 mg and 45 mg were selected on the totality of clinical safety, tolerability, and PK from the FIH study (Study 001); as well as toxicology and non-clinical pharmacodynamic (PD) data.

In Study 001, single ascending oral doses of VX-147 up to 50 mg and multiple ascending doses of VX-147 up to 45 mg once daily for 14 days were evaluated. The doses were well-tolerated and no clinically significant safety concerns were identified. In this study, a low dose of 15 mg once daily is selected to characterize the PK in FSGS patients and to assess any measurable decrease in proteinuria. Based on an exposure-response model, the exposures from the 15 mg dose are expected to result in approximately 90% inhibition in the in vitro ion flux model. This level of inhibition may result in a measurable decrease in proteinuria after 2 weeks of dosing.

A high dose of 45 mg once daily is selected to maximize the probability of reduction in proteinuria over the 11-week dosing period. Based on the exposure-response model referenced above, exposures from this dose are expected to result in over 96% inhibition in the in vitro ion flux model. VX-147 exposure from the 2 doses are expected to be well differentiated based on data from the FIH healthy subject study (Study 001). Thus, the doses selected will provide an adequate assessment of the dose-response relationship and safety profile of VX-147 in the exposure range of interest.

Additional information about FIH and nonclinical data are available in the Investigator's Brochure.

9.3.4 Study Assessments

All efficacy, safety, and PK assessments are common assessments for clinical studies, with the exception of those described below.

9.3.4.1 UPCR

Percent change from baseline in UPCR at Week 13 was chosen as the primary endpoint because proteinuria is a characteristic feature of FSGS and 1 of its main prognostic factors. Urine samples will be collected for UPCR using the first morning void, which is standardly used in clinical practice to determine accurate urine protein levels. As UPCR is variable within an individual, 3 samples will be taken during screening, Week 5, Week 9, and Week 13; and the average of the 3 values will be used to determine baseline, Week 5, Week 9, and end-of-treatment UPCR values, respectively.

9.3.4.2 SF-36

Change in SF-36 from baseline over the study treatment period will be assessed as an exploratory outcome. SF-36 is a patient-reported generic measure of health status. It has been previously used to evaluate health-related quality of life in patients with chronic kidney disease, including FSGS.^{22,23}

9.3.5 Use of Telemedicine for Study Visits

Telemedicine may be used for a number of study visits as detailed in Table 3-1 through Table 3-3. These visits will include home health nurse visits to the subject's home to complete assessments. All visits must have a consultation between the subject and investigator (i.e., in person, phone, or telemedicine video conference) within 1 business day after the home health visit, in order to check-in and collect AEs. Subjects and investigators may choose to conduct individual visits in the clinic or through use of home health. Periodic phone or telemedicine video visits may also be done to allow the investigator and subject to communicate directly; these visits may be done face-to-face in the clinic at the discretion of the investigator.

If local regulations or site practice do not allow telemedicine, all visits will be conducted at the site.

9.3.6 Eligibility Review

An independent, external expert with appropriate clinical and scientific background will evaluate the histopathological eligibility criteria to ensure that the subjects meet the study's definition of FSGS. Details of the process will be included in a separate procedure manual.

9.4 Prior and Concomitant Medications

Information about all prior and concomitant medications, including the subject's FSGS medications, other medications, and herbal and naturopathic remedies administered from 28 days before the Screening Visit through the SFUV or last off-treatment Follow-up Visit in Part B, whichever is later, will be recorded in each subject's source documents. For subjects who are screened but not subsequently enrolled, details of prior medication will only be documented in the subjects' source documents.

Subjects in Cohort 1 and Cohort 2 who are taking low dose systemic corticosteroids (i.e., ≤ 10 mg/day of prednisone or prednisone equivalent), ACE inhibitors, ARB, neprilysin inhibitor, SGLT2 inhibitor, a renin inhibitor, or certain immunosuppressants (tacrolimus, mycophenolate,

or cyclosporine) must remain on a stable medication regimen at least 28 days before the Screening Visit through the Week 13 or ETT (if applicable) Visit. Subjects in Cohorts 1 and 2 who are taking systemic corticosteroids must remain on a stable low dose from at least 28 days before the Screening Visit through the Week 13 or ETT (if applicable) Visit. Use of higher doses of corticosteroids are permitted to treat urgent comorbid medical conditions. During the Part B Off-Treatment Period, every effort should be made to avoid starting, stopping, or modifying doses of these medications. If it becomes clinically necessary to alter a subject's antihypertensive regimen during the study, changes to an antihypertensive medication dose or addition of a new antihypertensive medication are recommended before changes are made to any ACE inhibitor, ARB, neprilysin inhibitor, or renin inhibitor.

9.5 Study Restrictions

Study restrictions are summarized in Table 9-1. A nonexhaustive list of medications is provided in the Study Reference Manual.

Table 9-1 Study Restrictions

Restricted	Timing of Restriction			
Medication/Food/Activity ^a	Start	Stop		
Moderate and strong CYP3A4 inhibitors or inducers, including consumption of herbal medications (e.g., St. John's Wort)	None allowed within 14 days before the first dose of the study drug	Completion of Safety Follow-up Visit assessments		
Nonpermitted Immunosuppressants Note: This includes all immunosuppressants except tacrolimus, mycophenolate, and cyclosporine, which are permitted.	None allowed within 12 weeks before the first dose of study drug	Completion of the last study assessment		
Rituximab	None allowed within 6 months before the first dose of study drug	Completion of the last study assessment		
Other investigational drugs or devices	28 days before first dose of study drug, 5 half-lives before first dose of study drug dose, or time determined by local requirements (whichever is longer)	Completion of the last study assessment		
Creatine or creatine-containing dietary supplements	7 days before first dose of study drug	Completion of Safety Follow-up Visit assessments		
Grapefruit, grapefruit juice, pomelos, orange marmalade, Seville/blood oranges	7 days before first dose of study drug	Until last PK sample is taken		

^a See Section 9.4 for guidance on concomitant medications.

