Physical examination		X	A complete exam will be done if the visit occurs in the clinic. If the visit occurs using a home health nurse, an abbreviated exam will be done (Section 11.6.3).			

Table 3-1 Study VX19-147-101: Screening

Event/Assessment	Optional Genotype Screening Visit (Before Day -1)	Screening Period (Day -28 to Day -1)	Comments			
Serum FSH (suspected postmenopausal female subjects only)		X	A blood sample will be collected (Section 11.6.2).			
Serum β-hCG (all female subjects)		X	A blood sample will be collected (Section 11.6.2).			
Serum chemistry		X	A blood sample will be collected (Section 11.6.2).			
Hematology		X	A blood sample will be collected (Section 11.6.2).			
Coagulation		X	A blood sample will be collected (Section 11.6.2).			
Serology (HIV-1 and HIV-2 Antibodies)		X	A blood sample will be collected (Section 11.6.2).			
Hepatitis B surface antigen		X	A blood sample will be collected (Section 11.6.2).			
HCV test		X	A blood sample will be collected (Section 11.6.2).			
Confirmation of APOL1 genotype	X	X	A genotyping sample will be collected if a result is not available using a Vertex-approved clinical study assay (Section 9.1.1).			
Urine sample		X (3 samples)	Collected after signing the informed consent for use in efficacy, biomarker, and safety analyses (Sections 11.3 and 11.6.2). The first morning void will be collected for 3 independent samples, which are collected on 3 separate days within a 7-day period. The third sample must be collected by Day -5 to allow confirmation that UPCR values meet eligibility criteria (Section 8.1). Refer to sample handling guidelines to ensure samples are submitted appropriately for analysis.			
Adverse events	Continuous fron through		For subjects undergoing a 2-step screening process, AEs related to phlebotomy will be collected for up to 24 hours after the blood collection; AEs will not be collected during the time between a subject undergoing genotype screening and the start of the Screening Visit. Additional information about AE reporting is provided in Section 11.6.1.			

Protocol VX19-147-101, Version 6.0

Table 3-2 Study VX19-147-101: Part A Treatment Period 1, Treatment Period 2, and Early Termination of Treatment Visit

	Treatmen	t Period 1		Trea	atment Perio	od 2			
	Day 1 Visit	Week 1 Visit	Day 15 Visit	Week 3 Visit	Week 5 Visit	Week 9 Visit	Week 13 Visit	Early	

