9.1.1.2 Extension of Screening Period Window

A subject may have the Screening Period window extended by 2 weeks for the following reasons:

- Repetition of the Screening Period assessments (Section 9.1.1.1),
- Unexpected operational or logistic delays, or

If more than 42 days have elapsed from screening before first dose of study drug, all screening assessments need to be repeated.

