12.3.3.1 Analysis of Primary Variables

The primary efficacy endpoint is percent change from baseline in UPCR at Week 13. The Week 13 UPCR value will be calculated as the average of the available UPCR measurements (maximum 3) taken during Week 13. The baseline value will be the average of the 3 UPCR values from the urine samples collected during screening.

The percent change from baseline in UPCR at Week 13 will be analyzed by first log transforming the UPCR data before analyses to reduce skewness and calculating the change from baseline in log-transformed values. The GMPC from baseline in UPCR will be estimated along with the corresponding 2-sided 80% CI. The GMPC from baseline and associated confidence limits will be calculated by back-transforming the estimated simple mean of change from baseline in log-transformed data.

Sensitivity analyses for handling missing data due to treatment or study discontinuation will be described in the SAP.

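### Table 9-1 bars creatine only from 7 days before first dose, after most permitted UPCR baseline days, so baseline and Week 13 can be measured under different creatine rules

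*Protocol*

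**What the plan says.** All references are to Protocol Version 6.0 and the SAP.

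- **Restriction.** The Section 9.5 table (Table 9-1) lists "Creatine or creatine-containing dietary supplements". The restriction starts "7 days before first dose of study drug" and ends at "Completion of Safety Follow-up Visit assessments". Exclusion criterion 15 enforces the table only for the times the table gives, so it adds nothing earlier.
- **Baseline.** Section 12.3.3.1 states: "The baseline value will be the average of the 3 UPCR values from the urine samples collected during screening". SAP 9.1 agrees. Table 3-1 asks for three first morning voids on separate days within 7 days, and adds: "The third sample must be collected by Day -5 to allow confirmation that UPCR values meet eligibility criteria".
- **Window.** Section 9.1.1 places screening within 28 days before dosing. Section 9.1.1.2 adds: "A subject may have the Screening Period window extended by 2 weeks", with a 42-day limit.
- **No later substitute.** A footnote to Table 3-2 excludes the Day 1 urine from efficacy.
- **Drugs anchored to Screening.** Section 9.4 and inclusion criteria 7 and 8 require stable use from 28 days before Screening, but only for named classes: renin-angiotensin agents, neprilysin and SGLT2 inhibitors, corticosteroids and the permitted immunosuppressants. Creatine and other investigational drugs are not named.
- **Other investigational drugs.** Table 9-1 restricts these from the longest of "28 days before first dose of study drug, 5 half-lives before first dose of study drug dose, or time determined by local requirements" until "Completion of the last study assessment".

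**The concern.** UPCR has urine creatinine as its denominator. A restriction on creatine protects the endpoint only if it covers both ends of the comparison. As written, it covers every on-treatment void and almost no baseline void. A subject may comply fully, take creatine through the baseline voids, stop at Day -7, and be off it at Week 13.

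If creatine raises urine creatinine, baseline UPCR is understated. UPCR then rises when creatine stops, for a reason unrelated to VX-147, and the estimated reduction is biased towards no effect. There is no control arm in which the same shift would cancel. SAP 9.3.1.4 plans no sensitivity analysis that would show it.

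**Working it through.** **1. The plan's own precision.** Inputs from Section 12.1: SD 0.672 on the log scale, n = 10, 80% CI. Half-width = t(0.90, 9 df) × SD/√n = 1.383 × 0.672/√10 = 0.294, as stated. At an observed ratio of 0.60 the interval is 0.60 × exp(±0.294) = 0.447 to 0.805. This agrees with Table 12-1 within rounding (-55% to -19%). With n = 20 and the same SD, the half-width is 0.200.

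**2. Timing of creatine against baseline.**
- Ordinary screening: Day -28 to Day -5 is 24 possible baseline days. Day -28 to Day -8, 21 of the 24, precede the restriction.
- Extended screening: Day -42 to Day -5 is 38 days, of which 35 precede it.
- Possible sets of three separate days within 7 consecutive days, ordinary screening: 18 × C(6,2) + C(5,2) + C(4,2) + C(3,2) + C(2,2) = 270 + 10 + 6 + 3 + 1 = 290.
- Sets with all three days before the restriction (same count on 21 days): 15 × 15 + 20 = 245.
- Sets wholly inside the restriction: one (Days -7, -6, -5). So 289 of 290 have at least one void outside it.

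**3. Size in one subject.** The documents give no figure for the effect of creatine. Assume that it raises urine creatinine by a fraction x of 0.10 to 0.30 in all three baseline voids and not at Week 13.
- Baseline UPCR is multiplied by 1/(1 + x): 0.909 to 0.769, so 9% to 23% too low.
- Log shift in change from baseline = ln(1 + x): 0.095 to 0.262.
- A true ratio of 0.60 reads as 0.60 × (1 + x): 0.66 to 0.78, that is -34% to -22%.

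**4. Size in the estimate.** With k affected subjects out of n and a true -40% in all, the estimated ratio = 0.60 × exp[k × ln(1 + x)/n].

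| Affected | Estimate, x = 0.10 | Estimate, x = 0.30 |
|---|---|---|
| 1 of 10 (one cohort) | -39.4% | -38.4% |
| 2 of 10 (one cohort) | -38.8% | -36.8% |
| 1 of 20 (pooled primary analysis, SAP 9.3.1.2) | -39.7% | -39.2% |

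Against the half-widths in step 1, one subject in 10 shifts the log mean by 0.0095 to 0.0262, or 3% to 9% of 0.294. One in 20 shifts it by 0.0048 to 0.0131, or 2% to 7% of 0.200.

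**5. Other investigational drugs.** The restriction starts no later than Day -28.
- Ordinary screening: 0 of 24 baseline days precede it.
- Extended screening: Days -42 to -29, 14 of 38, can precede it if the 28-day term is the longest of the three.
- Residual exposure in ordinary screening: five half-lives are counted to first dose and not to baseline. As an illustration, assume a half-life of 5.6 days and a last dose at Day -28. The fraction left at Day -14 is 0.5^(14/5.6) = 18%. Over assumed half-lives of 1 to 8 days, the Day -14 residual runs from under 0.1% to 18%.

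**The case against.** The strongest objection concerns consequence. Prevalence of creatine use and its effect on urine creatinine are both assumed. The primary analysis pools about 20 subjects, so one user shifts it by less than one percentage point, in the conservative direction, against a planned interval of -55% to -19% even for a cohort of 10. This stands, and it limits the point to a cheap improvement.

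There is also partial mitigation. Section 9.4 records other medications and herbal and naturopathic remedies from 28 days before Screening, and Section 9.1.1 has subjects instructed on the restrictions beforehand. Neither bars creatine at baseline, and Section 9.4 does not name supplements, so capture is likely but not certain.

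A reader might infer two stronger points that the documents do not support.

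- *That baseline is routinely taken on another investigational drug.* In ordinary 28-day screening no baseline day precedes that restriction. Permitted dosing on a baseline day needs the two-week extension, granted only for stated reasons, and a drug whose half-life and local terms are short enough. Otherwise only residual exposure is possible, and its direction depends on the drug.
- *That nonpermitted immunosuppressants and rituximab share the fault.* Their restrictions start 12 weeks and 6 months before first dose. Even at Day -42 they are already barred on every possible baseline day. Whether the remaining interval before the voids is long enough is a clinical question that the documents do not settle.

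**Conclusion.** The creatine mismatch is confirmed from the text: 21 of 24 ordinary baseline days precede the restriction, every on-treatment void falls under it, and no other provision fills the gap. The timing is certain; the size is conditional. It rests on an assumed 10% to 30% rise in urine creatinine, affecting all three baseline voids and absent at Week 13, and on an unknown number of users.

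Under those assumptions the distortion is large for the individual but small in the estimate unless several subjects are affected. It would be wrong to conclude that the primary result is materially biased; the documents show only that the plan leaves the possibility open and has no analysis that would reveal it. For other investigational drugs the anchor and the baseline window do not match under the extension, which calls for reconciliation and no more.

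**What to change.** 1. In the creatine row of Table 9-1, count the existing 7 days back from the first screening UPCR void instead of the first dose. Add the same condition to the urine row of Table 3-1.
2. For subjects already enrolled, flag those with recorded creatine use at their baseline voids. Add to SAP 9.3.1.4 one presentation of the Week 13 geometric mean percent change without them, pooled and by cohort.
3. For other investigational drugs, reconcile Table 9-1, Section 9.1.1.2 and the baseline-void window. No interval is proposed here. The immunosuppressant and rituximab rows need no change on this account.

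**Cost.** Protocol and SAP wording, with no extra visits or samples. Creatine users start urine collection about a week later. A subject who stops at Day -28 could start at Day -21, still 16 days before the Day -5 deadline. Sample size and the 0.294 precision are unaffected. The flag can find only use that was recorded.

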9.6 Administration

VX-147 will be administered as 15 mg tablets, orally, as shown in Table 3-2.

Study drug will be administered according to the following guidelines:

- The first dose in each period must be administered under the supervision of site medical staff
 or a home health nurse. Subjects will be monitored for 4 hours after receiving the first dose
 of each Treatment Period
- On days of scheduled visits, the dose of study drug will be administered after predose assessments have been completed.
- Study drug will be taken at approximately the same time on each dosing occasion. For example, subjects that administer VX-147 dose at 8AM on Day 1 should administer all subsequent doses at 08:00AM ± 2 hours.
- Study drug may be taken with or without food.
- Subjects will swallow the study drug whole, with a full glass of water and will not chew it before swallowing.
- On days of intensive PK sampling, the date, dose taken, and time of study drug administration will be recorded for the 2 doses before PK sample collection and on the morning of PK sample collection.
- Subjects will be instructed to bring all used and unused materials associated with the study drug to the site or the nurse will take these materials at each study visit; study drug will be dispensed at each visit, as appropriate.

Missed Doses

If a subject misses a dose and recalls the missed dose within 6 hours, the subject should take his/her dose according to the guidance above. If more than 6 hours have elapsed after his/her usual dosing time, the subject should skip that dose and resume his/her normal schedule for the following dose. An example is provided below:

• If the morning dose of study drug should have been taken at approximately 08:00AM, and the subject remembers at 12:00PM that he/she forgot to take his/her dose, he/she should take the dose as soon as possible. If they remember after 2:00PM that they forgot to take the morning dose, they should skip that dose and resume the normal schedule the next day.

Additional information is provided in the Pharmacy Manual.

